14.3. Analysis Populations

Safety Population:

All subjects who were administered any test article excluding subjects who drop out prior to administering any test article. At least one observation should be recorded.

Per-Protocol Population:

All subjects who have successfully completed all visits and did not substantially deviate from the protocol as determined by the trial cohort review committee prior to database hard lock (Per-Protocol Population). Justification of excluding subjects with protocol deviations in the Per-Protocol Population set will be documented in a memo to file.

Intent-to-Treat (ITT) Population:

All randomized subjects regardless of actual treatment and subsequent withdrawal from study or deviation from protocol. At least one observation should be recorded.

14.4. Level of Statistical Significance

The primary analyses will be conducted with a 2-sided type I error rate of 5%.

14.5. Primary Analysis

The primary analysis will be conducted on the ITT population.

Absolute Rotation $\leq 10^\circ$

Absolute rotation data collected 15-minutes after insertion will be dichotomized as Y=1 if the absolute rotation is less than 10° and Y=0 otherwise for the purpose of analysis. Y will be analyzed using a generalized linear mixed model with a binary distribution and the logit as the link function. Sequence of lens wear, period and lens type will be included in the model as fixed effects. Other characteristics such as age may be included as covariates in the model. Site and subject will be included as random effects (G-side). The covariance measurements within the same subject (between eyes) across study periods will be modeled using an unstructured (UN) covariance structure. The Kenward and Roger method⁷ will be used for the denominator degrees of freedom. If none of the fixed effects are significant, the percentage of lens fits with absolute rotation less than 10° will be estimated by combining data from both lenses using 2-sided 95% confidence intervals.

The Model:

Let y_{ijklmn} denote the absolute rotation for the n^{th} eye from the m^{th} subject at the l^{th} site assigned to the k^{th} sequence during the j^{th} period for the i^{th} lens ($i=1,2$; $j=1,2$; $k=1, 2$; $l=1, \dots, l_m$; $n=1,2$). The likelihood will be constructed as follows:

$$\text{logit}(y_{ijklmn}) = \beta_0 + \beta_1 \text{Lens}_{i[j,k]} + \beta_2 \text{Period}_j + \beta_3 \text{Sequence}_k + \delta_l + \gamma_{l_m} + \varepsilon_{ijklmn}$$

Where:

- β_0 : Intercept

Clinical Study Protocol

Johnson & Johnson Vision Care, Inc.

- $Lens_i$: $Lens_i=1$ if Lens='-1.00DC'; otherwise $Lens_i=0$
- $Period_j$: $Period_j=1$ if period=1; otherwise $Period_j=0$
- $Sequence_k$: $Sequence_k=1$ if sequence=-1.00/-1.75; otherwise $Sequence_k=0$
- δ_l : effect of the l^{th} site, a random effect
- γ_{l_m} : effect of the m^{th} subject from the l^{th} site, a random effect
- ε_{ijklm} : Random error associated between eyes (left and right) for the m^{th} subject from the l^{th} site assigned to the k^{th} sequence during the j^{th} period for the i^{th} lens

Assume δ_l , γ_{l_m} and ε_{ijklm} are independent and

- $\delta_k \sim N(0, \sigma_{site}^2)$
- $\gamma_{l_m} \sim N(0, \sigma_{subject(site)}^2)$
- $$\begin{bmatrix} \varepsilon_{ijklm_Left} \\ \varepsilon_{ijklm_Right} \end{bmatrix} = \begin{pmatrix} [0] & \begin{bmatrix} \sigma_{11}^2 & \sigma_{12}^2 \\ \sigma_{21}^2 & \sigma_{22}^2 \end{bmatrix} \end{pmatrix}$$

Primary Hypothesis

The null and alternative hypothesis to test for superiority are as follows:

$$\begin{aligned} H_0: P_T &\leq 80\% \\ H_A: P_T &> 80\% \end{aligned}$$

Where P_T is the probability of the event (i.e., the probability of having absolute rotation less than 10° 15-minutes after insertion). Superiority will be concluded if the lower limit of the 95% confidence interval is above 80% (i.e., $P(p_{Test} > 80\%) \geq 0.975$).

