Objectives	
Primary Objective:
 
The primary objective of this study is to evaluate absolute rotation of the investigational multifocal toric lenses 15-minutes after insertion.
 
Exploratory Objectives:
 
Exploratory objectives include evaluations of absolute rotation at 1-, 3-, 7- and, 25-minutes and rotational stability with blink at 15- and 25-minutes. Additionally, initial comfort and handling scores will be assessed.

Study Endpoints	
Primary endpoint:
 
 • Absolute rotation less than or equal to 10° 15-minutes after insertion 
Exploratory endpoints:
 
 • Summary of Rotation 1-, 3-, 7- and, 25-minutes after insertion • Rotational stability with blink 15- and 25-minutes after insertion • Comfort scores approximately 30-minutes after insertion • Handling scores approximately 30-minutes after insertion

Clinical Study Protocol
Johnson & Johnson Vision Care, Inc.

Study Design	
The study is a bilateral, single-masked, single-visit, non-dispensing 2x2 crossover study. There will be eight study lens types, however, each subject will only be randomized to receive two study lens types.
 
 • Myopes with against-the-rule astigmatism will wear -3.00/-1.00 x 90 and -3.00/-1.75 x 90 • Myopes with with-the-rule astigmatism will wear -3.00/-1.00 x 180 and -3.00/-1.75 x 180 • Hyperopes with against-the-rule astigmatism will wear +3.00/-1.00 x 90 and +3.00/-1.75 x 90 • Hyperopes with with-the-rule astigmatism will wear +3.00/-1.00 x 180 and +3.00/-1.75 x 180 
The two lens powers that each subject wears are unlikely to be an exact match to their refractive error (ie. They may under-correct or over-correct the sphere and/or cylinder) and will therefore provide sub-optimal vision correction during the brief wearing period while rotation and comfort are evaluated. The wear period will be approximately forty (40) minutes per lens type.
 
See the flow chart at the end of the synopsis table for the schematic of the study visits and procedures of main observations (Figure 1).

Sample Size	Approximately 90 subjects who habitually wear soft contact lenses will be enrolled, with the aim that at least 80 will complete the study (40 myopes and 40 hyperopes).
Study Duration	The study will last approximately 2 months.

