2.2. Endpoints

Primary endpoint:

Absolute rotation $\leq 10^\circ$ (Acceptable Absolute Rotation)

Absolute rotation will be assessed at 1-, 3-, 7-, 15- and 25-minutes after insertion for each subject eye. However, absolute rotation at 15-minutes will be the primary endpoint. Acceptable absolute rotation is a binary response where Y=1 if absolute rotation is less than or equal to 10° and Y=0 otherwise (absolute rotation greater than 10°). See [REDACTED] in Appendix D for additional details on the collection of absolute rotation.

Exploratory endpoints:

- Summary of Rotation 1-, 3-, 7- and, 25-minutes after insertion
- Rotational stability with blink 15- and 25-minutes after insertion
- Comfort scores approximately 30-minutes after insertion
- Handling scores approximately 30-minutes after insertion

Comfort and handling scores will be assessed using the Contact Lens User Experience (CLUE™) questionnaire approximately 30-minutes after lens insertion. CLUE™ is a validated patient-reported outcomes questionnaire to assess patient-experience attributes of soft, disposable contact lenses (comfort, vision, handling, and packaging) in a contact-lens wearing population in the US, ages 18-65. Derived CLUE™ scores using Item Response Theory (IRT) follow a normal distribution with a population average score of 60 (SD 20), where higher scores indicate a more favorable/positive response with a range of 0-120. A 5-point increase in an average CLUE™ score translates into 10% shift in the distribution of scores for population of soft contact lens.⁹

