2.3. Hypotheses

Primary Hypothesis

1. Approximately 15-minutes after lens insertion, the percentage of lens fits with absolute rotation less than or equal to 10 degrees will be superior to 80%.

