14.2. Sample Size Justification

This study was designed and powered to test that the percentage of lens fit with absolute rotation for both study lenses is superior to 80% 15-minutes after insertion. The sample size

Clinical Study Protocol

Johnson & Johnson Vision Care, Inc.

was calculated using a 2-sided type I error rate of 5% with at least 80% statistical power. Historical data from [REDACTED] and [REDACTED] was both utilized in estimation of the sample size.^{7,12} Table 6 below provides details regarding each clinical study and Table 7 summarizes the absolute rotation for each study and lens for all lens fits (including any modifications).

Table 6 Summary of Historical Clinical Studies

Study ID	Design	Population	Age Range (years)	Number Enrolled	Number Dispensed	Number Completed
[REDACTED]	Single arm	Hyperopes + Myopes	40 to 70	95	86	84
[REDACTED]	2x2 crossover	Myopes	18 to 39	103	98	93

Table 7 Summary of Absolute Rotation by Lens – 15-Minutes After Insertion

	AOFA N=202	Aurora A		
		Hyperopes N=114	Myopes N=136	Total N=250
Absolute rotation n(%)				
0 to 5	174 (86.1)	85 (74.6)	96 (70.6)	181 (72.4)
>5 to 10	19 (9.4)	14 (12.3)	21 (15.4)	35 (14.0)
>10 to 15	8 (4.0)	7 (6.1)	11 (8.1)	18 (7.2)
>15	1 (0.5)	8 (7.0)	8 (5.9)	16 (6.4)
Total	202	114	136	250
Absolute rotation < 10° n(%)				
Yes	193 (95.6)	99 (86.8)	117 (86.0)	216 (86.4)
No	9 (4.5)	15 (13.2)	19 (14.0)	34 (13.6)
Total	202	114	136	250

N=Number of lens fits.

Based on the results from [REDACTED], the lens design was modified to improve the absolute rotation. The changes implemented into the lens design are more closely aligned with the Acuvue Oasys for Astigmatism lens design utilized in [REDACTED]. However, as indicated in Table 5, [REDACTED] enrolled non-presbyopic myopic subjects only. In general, presbyopic subjects have been found to more contact lens rotation compared to non-presbyopic subjects, therefore,

Clinical Study Protocol **Johnson & Johnson Vision Care, Inc.**

results from both studies were considered when choosing different scenarios of reference rates.^{7,12}

Shown in Table 6 above, [REDACTED] had rates of 86% and 96%, respectively. Therefore, different scenarios used for the sample size and power calculations were chosen within that range. Furthermore, taking into consideration that this study will enroll subjects aged 40 to 70, more conservative rates of 88%, 89% and 90% were used.^{7,12}

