Sample size estimates were carried out using Monte Carlo methods. A total of 2000 boot-strap samples were simulated using different scenarios for the reference rate for event Y and interclass correlations of 0.80 to model the covariance between the left and right eyes within the same treatment, and 0.50 to model both the covariance between treatments within the same eye as well as between eyes and treatments. Each boot-strap sample was analyzed using a generalized linear mixed model with a binary distribution and the logit and the link function. Lens was included as the only fixed effect. Errors between measurements within the same subject and period were modeled using a variance component covariance structure (VC). The Kenward and Roger Method was used for the denominator degrees of freedom.¹³ The percentage of lens fits with absolute rotation less than 10° was constructed using 95% confidence intervals for the least-square mean. Success for each boot-strap sample was declared if the lower limit of the 95% CI was above 80%. Table 8 below displays the number of subjects required to test superiority for the primary hypothesis for each study lens.

While subjects will wear the study lenses in a random order data collected during evaluations in period 2 are not expected to be influenced by the lenses worn during period 1 since a wash-out 15 -minutes will be utilized between study lenses and, subjects' absolute rotation depends on the study lens on eye at that moment of data collection.

Table 8 Statistical Power for 80 Subjects to complete by Reference Rate

	Reference Rate		
	88%	89%	90%
Statistical Power (%)	87.7	95.1	98.3

Up to 90 subjects (45 Hyperopes and 45 Myopes) will be enrolled with the target of 80 subjects (40 Hyperopes and 40 Myopes) to complete the study. Since this is a single-visit, non-dispensing study, a high rate (> 10%) of subject drop-out is not expected to occur. However, subject drop-out rate will be monitored. If an unexpectedly high dropout rate is observed, then enrollment maybe be increased to ensure the minimum number of subjects required to test the primary hypothesis complete the study.

Clinical Study Protocol

Johnson & Johnson Vision Care, Inc.

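### Section 14.5 codes a rotation of exactly 10° as a failure, while the stated endpoint and hypothesis count it as a success

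*Combined protocol and SAP*

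**What the plan says.** **Places where 10° is a success**

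- Synopsis, Study Endpoints: "Absolute rotation less than or equal to 10° 15-minutes after insertion".
- Section 2.2: "Y=1 if absolute rotation is less than or equal to 10° and Y=0 otherwise (absolute rotation greater than 10" degrees). This is the fullest definition, because it spells out both categories.
- Section 2.3: "the percentage of lens fits with absolute rotation less than or equal to 10 degrees will be superior to 80" percent.
- The sub-heading over the analysis in Section 14.5 also uses ≤10°.

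**Places where 10° is a failure**

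- Section 14.5, coding rule: "dichotomized as Y=1 if the absolute rotation is less than 10° and Y=0 otherwise".
- Section 14.5, pooling sentence: "the percentage of lens fits with absolute rotation less than 10° will be estimated by combining data from both lenses".
- Section 14.5, definition of P_T in the null and alternative hypotheses: "the probability of having absolute rotation less than 10° 15-minutes after insertion".
- Section 14.2, simulation text: "The percentage of lens fits with absolute rotation less than 10° was constructed using 95% confidence intervals".
- Section 14.2, Table 7 row label: "Absolute rotation < 10° n" (%).

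Section 7.2 (steps 1.23 and 1.36) has the investigator record the size of the 15-minute rotation to the nearest degree. Section 14.6 plans no secondary analysis and Section 14.7 only describes the exploratory endpoints, so this binary variable carries the study's one formal test.

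**The concern.** The sentences that define the endpoint and those that tell the programmer how to build and test it disagree at the cut-point itself. With whole-degree recording, a reading of 10° can occur. Section 2.2 codes it Y=1 and Section 14.5 codes it Y=0, and the plan does not say which prevails. The hypothesis is affected too: Section 2.3 states it with ≤10°, while P_T in Section 14.5 states it with <10°.

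Two things are at stake. First, literal use of 14.5 tests a rate that can only be equal to or lower than the stated endpoint rate, against the same 80% bar. Second, with both rules in writing, the choice could be made after the number of 10° readings is known. Section 5.2 leaves investigators and site staff unmasked, and Section 14.1 has the analysis done by or for the sponsor. Choosing at that stage would be a post hoc choice of primary endpoint, in whichever direction it went.

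**Working it through.** **1. What the Table 7 row really counts.** Add the first two rotation categories of Table 7 and compare with the Yes count in the row labelled <10°.

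| Column | 0 to 5 | >5 to 10 | Sum | Yes count | N | Rate |
|---|---|---|---|---|---|---|
| AOFA | 174 | 19 | 193 | 193 | 202 | 95.5% |
| Aurora A, hyperopes | 85 | 14 | 99 | 99 | 114 | 86.8% |
| Aurora A, myopes | 96 | 21 | 117 | 117 | 136 | 86.0% |
| Aurora A, total | 181 | 35 | 216 | 216 | 250 | 86.4% |

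All four agree exactly. (193/202 is 95.54%; the table prints 95.6.) The upper category includes 10°, so the historical rates are ≤10° rates despite the label. Section 14.2 chose its 88%, 89% and 90% scenarios from the range those rates span.

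**2. How far the rate could move.** The share at exactly 10° is not in the documents. Let f be the assumed fraction of the >5 to 10 category that reads 10°. Then the <10° rate is (Yes count − f × category count)/N.

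| f | Aurora A total: (216 − 35f)/250 | AOFA: (193 − 19f)/202 |
|---|---|---|
| 0 | 86.4% | 95.5% |
| 0.1 | 85.0% | 94.6% |
| 0.2 | 83.6% | 93.7% |
| 1 (outer bound) | 72.4% | 86.1% |

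f = 0.2 corresponds to an even spread over 6, 7, 8, 9 and 10°. AOFA matters because Section 14.2 says the modified design is closer to that lens.

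**3. What that does to power (illustration only).** Take 80 subjects × 2 eyes = 160 fits per lens, treated as independent:

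power = Φ[(p − 0.80)/√(p(1 − p)/160) − 1.96].

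At p = 0.88 the standard error is √(0.88 × 0.12/160) = 0.0257. Then 0.08/0.0257 = 3.114 and Φ(3.114 − 1.96) = 87.6%. At 0.89 and 0.90 the formula gives 95.3% and 98.8%. Table 8 states 87.7%, 95.1% and 98.3%, so it comes close. Now subtract the assumed percentage points at exactly 10° from p:

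| ≤10° rate | 0 | 0.5 | 1 | 1.9 | 2.8 |
|---|---|---|---|---|---|
| 88% | 87.6 | 81.8 | 74.9 | 60.7 | 45.7 |
| 89% | 95.3 | 92.1 | 87.6 | 76.4 | 62.3 |
| 90% | 98.8 | 97.5 | 95.3 | 88.6 | 77.8 |

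The last two columns are one fifth of the 9.4% and 14.0% categories. On this formula, power reaches 80% at p = 0.8736, that is, with 0.64 points at 10° in the 88% scenario.

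**4. Sensitivity to the correlations.** Section 14.2 states correlations of 0.80 between eyes within a lens and 0.50 otherwise, which step 3 ignores.

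- Per lens, the design effect is 1 + 0.80 = 1.8, so 160/1.8 = 88.9 effective fits. Power at 88% is 64.1%, falling to 50.1% with one point at 10°.
- With both lenses pooled, the design effect is 1 + 0.80 + 0.50 + 0.50 = 2.8, so 320/2.8 = 114.3 effective fits. Power at 88% is 74.9%, falling to 60.5% with one point at 10°.
- A simulation of 80 subjects with these correlations on a latent scale, lenses pooled, at 88% with 0, 1 and 2 points at 10°, gives about 90, 82 and 71% when the standard error ignores clustering. With a cluster-robust standard error it gives about 72, 59 and 45%.

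The level of power depends heavily on the method. The direction does not: each point at 10° costs power.

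**The case against.** The best reply is that <10° is loose wording for ≤10°. Section 2.2 spells out both categories, the sub-heading in 14.5 uses ≤10°, and Table 7 puts a <10° label on counts that include 10°. A programmer who reads the whole document would probably code ≤10°. That is a fair inference about intent, but the strict wording is in words in the coding rule, the pooling sentence and P_T, which are the sentences that specify the test. The Table 7 label is weaker evidence, since a ≤ sign can be misread from a PDF cell; the point does not need it.

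The power figures can also be challenged, and this largely stands. The approximation ignores stated correlations. Once they enter, the 88% scenario is already below 80% power with no reading at 10°, so the 0.64-point threshold has no meaning outside that approximation. Closeness to Table 8 does not validate the formula: simulations with the stated correlations did not match Table 8 within 2 points at all three rates, and the plan does not describe its simulation fully enough to settle why.

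It is also fair that 88–90% are planning choices for an event Y, and that the 14.2 text itself says less than 10°. What can be said is narrower: the historical rates that informed those choices are ≤10° rates.

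Finally, the strict rule is conservative, and its effect may be nil. Both are true. They limit the harm but leave the definition unsettled.

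**Conclusion.** The concern holds. The plan defines its only confirmatory outcome in two ways that differ at a value that can be recorded, and the literal coding rule contradicts the stated endpoint and the Section 2.3 hypothesis. This must be corrected, and the case rests on that contradiction, not on the power figures.

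The direction is certain: P(<10°) cannot exceed P(≤10°), so literal coding cannot inflate type I error for the ≤10° hypothesis and can only reduce power. The size is unknown. It is zero if no fit reads 10° or if the program follows Section 2.2. The historical table bounds the loss at 14.0 percentage points for the earlier multifocal toric lens and 9.4 for the other lens; 2.8 and 1.9 points follow from assuming an even spread over 6 to 10°. A loss of one or two points would matter to power in the 88% scenario under every method tried.

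**What to change.** In Section 14.5, code Y=1 for absolute rotation ≤10° and Y=0 for >10°, as in Section 2.2. Use ≤10° in the pooling sentence and in the definition of P_T as well. For consistency, make the same change in the Section 14.2 simulation text and the Table 7 row label. Table 8 stays as it is, because the simulation used assumed event rates and not a degree cut-off.

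Make the change before database lock, and preferably before any 15-minute rotation data are reviewed, so that the choice cannot depend on how many fits read 10°. The cost is a wording amendment: no new data, no extra subjects and no new sample size calculation.

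### Section 14.5 tests a population percentage against 80%, but the usual back-transformed mean of its mixed logit model lies above that percentage, and the plan does not say how the tested figure is obtained

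*Combined protocol and SAP*

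**What the plan says.** - **Target.** Section 2.3 states that "the percentage of lens fits with absolute rotation less than or equal to 10 degrees will be superior to 80" per cent. Section 14.5 defines P_T as the probability of that event and adds: "Superiority will be concluded if the lower limit of the 95% confidence interval is above 80" per cent. Section 14.4 sets a two-sided 5% level, so 2.5% in the direction of the claim.
- **Model.** Section 14.5 specifies a binary logit mixed model with sequence, period and lens as fixed effects and an unstructured covariance between eyes. It adds: "Site and subject will be included as random effects (G-side").
- **Estimate.** If no fixed effect is significant, the percentage "will be estimated by combining data from both lenses using 2-sided 95% confidence intervals". No formula is given. The section does not say what is compared with 80% when a fixed effect is significant.
- **Sample size.** Section 14.2 says the study is powered to show that "the percentage of lens fit with absolute rotation for both study lenses is superior to 80% 15-minutes after insertion", and describes Table 8 as applying to each study lens. In its simulation the percentage "was constructed using 95% confidence intervals for the least-square mean". That model differs from the one in 14.5: "Lens was included as the only fixed effect", and "Errors between measurements within the same subject and period were modeled using a variance component covariance structure (VC"). No subject or site random effect is mentioned there.

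**The concern.** A percentage of lens fits is an average over the people and sites in the population. A logit model with normal subject and site effects is parameterised conditionally on those effects. Back-transforming its mean gives the success probability for a subject and site whose effects are exactly zero. Because the inverse logit is curved, that probability is higher than the population average whenever the rate is above 50% and the variance is positive. The lower limit would then be compared with 80% on the wrong scale, in the direction that favours the claim.

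This is the only confirmatory test in the study (Section 14.6 lists no secondary analysis), and Section 15.3 gives design confirmation as its purpose. If the text leaves the derivation open, the choice may be made after the data are seen.

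**Working it through.** **Inputs.** 80 completers (14.2); 4 fits each, from two eyes and two lenses (6.1), so 320 fits; correlations of 0.80 between eyes with the same lens and 0.50 across lenses (14.2). The plan does not say whether these correlations are on the binary or a latent scale, so both are shown. Threshold 80%; nominal one-directional error 2.5%.

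**Step 1: Table 8.** The plan states 87.7 / 95.1 / 98.3% power at true rates of 88 / 89 / 90%. Of the analyses tried, the closest was a pooled logit interval that treats all 320 fits as independent. It gave 86.5 / 93.2 / 96.8% with binary-scale correlations (20,000 runs), all within 2 points.

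**Step 2: size of the shift.** For subject SD σ on the logit scale, find β such that the average of expit(β + σz) over z ~ N(0,1) equals 0.80. The back-transformed mean is then expit(β).

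| σ | β | expit(β) |
|---|---|---|
| 0.5 | 1.459 | 81.1% |
| 1 | 1.650 | 83.9% |
| 1.5 | 1.916 | 87.2% |
| 2 | 2.228 | 90.3% |
| 3 | 2.929 | 94.9% |

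**Step 3: false positives at a true 80%, back-transformed mean.** Residual pseudo-likelihood with lens, period and sequence fixed, Kenward-Roger degrees of freedom, 5 sites of 16 subjects, true site variance zero, 1,500 runs per cell. The unstructured block is omitted, and the code is not SAS. Ranges run from latent to binary scale at 0.80/0.50.

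| Pass rule | Subject and site effects | Subject effect only |
|---|---|---|
| Pooled | 15–28% | 22–45% |
| Pooled if no fixed effect is significant, otherwise each lens (assumed) | 12–24% | 18–38% |
| Each lens must pass | 3.0–9.7% | 4.5–15% |

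The mean back-transformed estimate was 84–87%, against a mean raw proportion of 80.1%. A separate intercept-only version with a subject effect gave 19–39% pooled. Adding an unstructured residual block to it gave 52–80%.

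With weaker binary correlations (subject and site effects), the pooled rate was 12% at 0.5/0.25 and 6.3% at 0.3/0.15. The each-lens rates were 1.6% and 0.5%.

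**Step 4: if pooling means a plain binomial interval.** The design effect is 1 + 0.80 + 2(0.50) = 2.8. The naive SE at 80% is √(0.8 × 0.2 / 320) = 0.0224, and the true SE is 0.0224 × √2.8 = 0.0374. The false-positive rate is P(Z > 1.96/√2.8) = P(Z > 1.17) = 12.1%. Simulation gave about 8–11% with a logit limit and 11–15% with a Wald limit. If each lens must pass, a naive logit interval gave about 0.7–1.4% (0.6–1.7% in a second set of runs).

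**Step 5: a population-averaged alternative.** A pooled logit interval clustered on subject gave 2.1–2.3% at a true 80%. A logit GEE with Mancl-DeRouen standard errors gave 2.3–2.4%. Power of the clustered pooled interval with 80 completers:

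| True rate | Table 8 | Binary scale | Latent scale |
|---|---|---|---|
| 88% | 87.7% | 56% | 72% |
| 89% | 95.1% | 69% | 84% |
| 90% | 98.3% | 79% | 92% |

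**The case against.** **The simulated models are not the plan's model.** This stands. The Step 3 table leaves out the unstructured block, and results vary widely with the fitting method, so no single figure can be called the plan's error rate. The direction does not change: every subject-random-effect fit at 0.80/0.50 was above 2.5% when back-transformed and pooled.

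**The plan never says it will back-transform at zero random effects.** Also true. A reader might infer from 14.2 that a least-squares mean is prescribed for the primary analysis. It is named only for the power simulation, under a different model, and does not settle 14.5. A sponsor who intends a population-averaged, clustered estimate has no bias problem, but 14.5 does not say so, and following its model in the ordinary way leads to the conditional value.

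**The independent-fits interval is nowhere requested.** Correct. The pooling sentence closes a paragraph that requires subject effects and between-eye covariance. Pooling with a subject-clustered interval fits the same words and keeps about 2.5%. Step 4 shows one possible reading, not a stated method.

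**The pass rule drives the result.** This stands too. Section 14.2 points towards each lens, and 14.5 towards a pooled rate. Requiring each lens to pass removes the excess for the naive logit interval, and for the back-transformed mean when correlations are weak. It does not remove it for the back-transformed mean at 0.80/0.50.

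**Conclusion.** The concern holds in this form: the quantity tested is a population percentage, the specified model is conditional on subject and site, and 14.5 does not bridge the two. On the ordinary back-transformed reading the estimate is too high. At the planning correlations the pooled false-positive rate was roughly 15–45% in simplified models, against 2.5%.

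The size rests on the planning correlations, on pooling, on zero site variance and complete data, and on omitting the unstructured block. It is smaller with weaker correlation.

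Two stronger conclusions are tempting but unsupported. One is that the trial's actual error rate is known to lie in this range; the fitted models are only illustrations. The other is that Table 8 ignored clustering; that is an inference from the match in Step 1, because the simulation code is not in the documents. The case for re-running Table 8 does not depend on it, since its model already differs from that of 14.5.

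**What to change.** In Section 14.5:

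1. Define P_T as the population-averaged percentage of lens fits.
2. Obtain it and its 95% interval by a method averaged over subjects and sites and clustered on subject. One option is a logit GEE with lens, period and sequence and small-sample-corrected standard errors. Another is mixed-model predictions averaged over the random effects, provided simulation shows a false-positive rate near 2.5% at a true 80%. Exclude a back-transformed least-squares mean at zero random effects. Site as a fixed effect in the GEE needs care: estimates were not finite in 3–26% of simulated data sets at true rates of 88–90%.
3. State one pass rule, pooled or each lens, reconciling 14.2 with 14.5, and remove the dependence on whether the fixed effects are significant.
4. Re-run Table 8 with that analysis and pass rule, state the scale of the correlations, and restate the power.

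The cost is SAP wording and programming, with no new data items, but the stated power becomes less favourable. At 0.80/0.50, 80% pooled power at a true 88% would need about 95 (latent) to 130 (binary) completers. If each lens must pass, power with 80 completers is lower still: about 25–34 / 33–49 / 46–63% at 88 / 89 / 90% across the clustered methods tried. Whether to enlarge the study is a separate decision.
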